Exploratory Aim: The analyses performed in this aim will reveal 1) how a preoperative exercise intervention effects subjective and objective measures of psychological stress, autonomic function, and systemic inflammation prior to and after surgery, and 2) whether these preoperative measures predict postoperative outcomes in patients with pancreatic cancer undergoing neoadjuvant treatment. These analyses will also illustrate typical changes in measures of physical fitness and physical function through analysis of the Standard Care group. Results from this aim may also lead to the development of novel interventions, if measures are predictive of outcomes but not adequately changed by exercise.

Outcomes from this study will add to the growing body of literature on the effectiveness of preoperative exercise programs in cancer survivors, as well as demonstrate the potential effectiveness of an exercise intervention in patients with pancreatic cancer, where there is limited evidence. By examining potential mediators in the effectiveness of exercise on postoperative outcomes, it allows future studies to tailor exercise program components to focus on the mediators most strongly associated with positive outcomes.

H. References:

- 1 Jemal, A. *et al.* Global cancer statistics. *CA Cancer J Clin* **61**, 69-90, doi:10.3322/caac.20107 (2011).
- 2 Schmitz, K. H. *et al.* American College of Sports Medicine roundtable on exercise guidelines for cancer survivors. *Medicine and science in sports and exercise* **42**, 1409-1426, doi:10.1249/MSS.0b013e3181e0c112 (2010).
- 3 Saif, M. W. Controversies in the adjuvant treatment of pancreatic adenocarcinoma. *JOP* **8**, 545-552 (2007).
- 5 Chandrabalan, V. V. *et al.* Pre-operative cardiopulmonary exercise testing predicts adverse post-operative events and non-progression to adjuvant therapy after major pancreatic surgery. *HPB (Oxford)* **15**, 899-907, doi:10.1111/hpb.12060 (2013).

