The potential participant population will be individuals who receive a diagnosis of borderline-resectable pancreatic cancer (adenocarcinoma), being treated at the University Hospital Cancer Center. These inclusion and exclusion criteria will apply to participants in both groups.

Inclusion Criteria: Recent (< 4 week) first diagnosis of a borderline-resectable pancreatic adenocarcinoma, assigned to receive neoadjuvant therapy and surgery at University of Colorado Cancer Center, physician clearance to participate in exercise program, and age 21-80 years.

Exclusion Criteria: Any significant comorbid conditions that would interfere with or preclude participation in an exercise intervention, including orthopedic conditions such as advanced osteoarthritis, mobility-limiting amputations or chronic injuries, or mobility-limiting acute orthopedic injuries; advanced rheumatoid arthritis; widespread chronic pain conditions such as fibromyalgia; pulmonary conditions such as chronic obstructive pulmonary disease, emphysema, interstitial lung disease, use of supplemental oxygen; known cardiovascular disease, uncontrolled hypertension, or new cardiac event within the past 6 months. Participants with a second cancer diagnosis at the time of enrollment will be excluded.

Sample size estimation: No studies have previously investigated the effects of preoperative exercise in patients with pancreatic cancer. In patients with lung cancer, a preoperative exercise program reduced hospital length of stay by 4 days compared to usual care⁴⁰. Based on this difference, with a SD of 3, 12 participants would be required in each the experimental and control groups ($\alpha = 0.05$, $\beta = 0.90$ ⁴¹). To account for overall attrition, groups will be increased by 3 participants each, based on a study of preoperative exercise after neoadjuvant treatment in patients with rectal cancer showing an overall attrition of 28%⁴². A total of **30 participants (15 per group)** will be recruited for this study.

C. Study Design and Research Methods

This is a prospective, non-randomized, parallel group, intervention control trial, patterned on a similar pilot study in patients with rectal cancer⁴².

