Recruitment: Participants will be recruited from the University Hospital Cancer Center. Patients with a recent diagnosis (< 4 weeks) of pancreatic cancer will be given information on the study by their treating physicians and asked if they would be interested in participating. If yes, physicians will have patients complete a HIPAA A form to provide study personnel with their name. Study personnel will access the patients' medical records to evaluate the inclusion/exclusion criteria. If these criteria are met, research personnel will meet with the

potential participant at the University of Colorado Cancer Center to provide information about the study. If patients are still interested in participating, the familiarization and possibly first visit will be scheduled. Participants will have the option of combining the familiarization session and Visit 1. All data collected during screening will be destroyed and recollected after obtaining written consent in patients choosing to participate. If the inclusion/exclusion criteria are not met after review of the health record, the patient will be contacted and the exclusion decision will be explained.

Group Assignment: Volunteers meeting the inclusion and exclusion criteria and willing to participate in the exercise intervention will be assigned to the exercise group. The standard of care, non-exercise control group will comprise volunteers who meet the inclusion and exclusion criteria but are unable to commit to participation in the exercise intervention for practical reasons (e.g. barriers in transportation or home location). The use of a non-randomized study design is to maximize patients participating in the exercise program to determine accrual rate, program adherence, and safety while still allowing a non-exercise control group.

Protocol:

[figure not shown]

Figure 1

Figure 1 shows the event timeline of the study, with time points of visits and intervention in relation to diagnosis and surgery. Written informed consent will be obtained by a study investigator during a familiarization period, where participants will have assessments and the exercise investigation explained in-depth. There will be four time points for data collection: pre-intervention (Visit 1), post-intervention and preoperative (Visit 2), 30-day postoperative (data retrieved from electronic health record), and follow-up (Visit 3).

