The timeline for this protocol is estimated at 2 years. Data collection (participant recruitment and intervention) is estimated at 1 - 1.5, after which data will be analyzed and manuscripts prepared.

Data Analysis and Anticipated Outcomes: Groups will be compared on demographic variables such as age and gender. Variables that differ significantly will be included in planned analyses as covariates. Statistical significance will be defined as $\alpha \leq 0.05$, however, results will be interpreted cautiously as is warranted for pilot studies⁴⁴. As we expect to be underpowered to test for statistical interactions, multiple tests will be used to assess differences in baseline measures, change scores, and postoperative outcomes between groups. Change scores will be calculated as the difference between Visit 2 and Visit 1. Groups will be compared using non-parametric exact k-sample permutation tests, which are well suited for small sample sizes as they do not rely on typical normal-theory methods⁴⁵.

Aim 1: The feasibility of implementing this intervention will be assessed by quantifying the accrual rate of patients willing and able to participate in the preoperative exercise intervention and individual patients' adherence to the prescribed exercise program (percentage of scheduled sessions attended). Safety will be determined by the number of non-serious and serious adverse events and relatedness of the events to exercise, as described by COMIRB.

Aim 2: Hypothesis 1 – Baseline physical fitness and function measures and change scores will be compared between groups using exact k-sample permutation tests. We anticipate a significant difference in the changes from Visit 1 to Visit 2, with the Exercise group demonstrating maintained or improved physical fitness and function compared to the Control group, with no differences in baseline measures. A secondary analysis will be used to describe the trajectory of changes in physical function from visits 1, 2, and 3.

Hypothesis 2 – Postoperative outcomes will be compared with exact k-sample permutation tests (hospital length of stay) or Fisher's exact tests (hospital readmission) between the Exercise and Control groups. We anticipate the Exercise group to have a significantly lower hospital length of stay and occurrence of hospital readmission compared to the Control group.

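### The sample-size statement mislabels power as β, and 12 evaluable patients per group give about 88% power, not 90%, at the plan's own inputs (less if the groups are unequal)

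*Combined protocol and SAP*

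**What the plan says.** The sample-size paragraph in section IV.B takes its effect from a lung cancer study in which "a preoperative exercise program reduced hospital length of stay by 4 days compared to usual care". It continues: "Based on this difference, with a SD of 3, 12 participants would be required in each the experimental and control groups". The error rates are given as "\alpha = 0.05$, $\beta = 0.90". The attrition allowance follows: "To account for overall attrition, groups will be increased by 3 participants each", making 15 per group and 30 in total. The paragraph names neither the formula nor the sidedness.

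The Data Analysis Plan (IV.F) sets the threshold: "Statistical significance will be defined as $\alpha \leq 0.05". It compares groups, for length of stay as for other continuous outcomes, with "non-parametric exact k-sample permutation tests, which are well suited for small sample sizes".

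Under Group Assignment (IV.C), eligible volunteers who are "willing to participate in the exercise intervention will be assigned to the exercise group". Eligible volunteers who cannot commit for practical reasons, such as transport or where they live, form the control group. No quota or cap is described for either group.

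**The concern.** There are three defects in one sentence of the plan.

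- **Label.** β is the type II error rate, so 0.90 cannot be what was meant.
- **Method.** The 12 per group appears to come from a formula that treats the SD as known. The planned analysis is a small-sample test, for which that formula is slightly optimistic.
- **Balance.** The calculation assumes equal groups, but the sizes depend on who can attend. The stated reason for not randomising is to get as many patients as possible into the exercise programme, which pulls away from 1:1.

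What is at stake is the accuracy of the planning statement. The protocol expects the results to support adequately powered later studies, and those who plan them will read this paragraph.

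**Working it through.** **Inputs.** Difference 4 days, SD 3 days, α = 0.05 and 12 per group (all IV.B). The standardised difference is d = 4/3 = 1.333. Sidedness is not stated. Two-sided is taken because it reproduces the plan's figure: the one-sided normal formula gives 9.63, so 10 per group.

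**Step 1: reproduce the plan's figure.** With the normal formula and power 0.90,

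n per group = 2(1.960 + 1.282)² / (4/3)² = 11.82, rounded up to 12.

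Power at 12 by the same formula is Φ(1.333 × √(12/2) − 1.960) = Φ(1.306) = 90.4%. The plan's 12 is therefore reproduced. With β = 0.90 taken literally (power 0.10), the formula gives 0.52, so 1 per group. The label is wrong and the intended value is clear.

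**Step 2: allow for the small sample.** A two-sample t test has noncentrality d / √(1/n₁ + 1/n₂) on n₁ + n₂ − 2 degrees of freedom.

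- 12:12: noncentrality 3.266, critical t 2.074 on 22 df, power 87.7%.
- 13:13: noncentrality 3.399, critical t 2.064 on 24 df, power 90.3%.

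Solving for 90% gives 12.86, so 13 per group.

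**Step 3: the planned test.** A two-sided permutation test of the difference in means was simulated on normal data (3,000 trials, 999 permutations each). Power was 87.5% at 12:12 and 90.8% at 13:13, with a Monte Carlo standard error of about 0.6 points at 12:12. This agrees with the t test to within simulation error.

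**Step 4: unequal groups.** The total is held at 24 evaluable and the splits are assumed for illustration; the documents give none.

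| Split | Noncentrality | Two-sided t-test power |
|---|---|---|
| 12:12 | 3.266 | 87.7% |
| 14:10 | 3.220 | 86.8% |
| 16:8 | 3.079 | 83.7% |
| 18:6 | 2.828 | 77.1% |

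The simulated permutation test gives 83.6% at 16:8 and 77.5% at 18:6.

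**Step 5: no attrition.** If all 30 recruits are evaluable, t-test power is 94.1% at 15:15, 91.3% at 20:10 and 87.6% at 22:8 (the unequal splits again assumed).

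**Optional sensitivity.** For assumed SDs of 4, 5 and 6, t-test power at 12:12 is 65%, 47% and 35%. No figure in the documents supports this range.

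**The case against.** The strongest reply is that 12 is not a mistake. The plan names no formula, a standard one returns exactly 12 with 90.4% power, and the t-based answer differs by one patient per group. A one-sided t test would give 93.6% at 12:12. The plan also recruits 15 per group, so 12 is the number left after the attrition allowance. Most of this stands. The 12 is an approximation, and the gap at 12:12 is between two and three percentage points. The one-sided reading helps less, because the plan declares no one-sided test and the one-sided normal formula does not give 12.

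A reader might infer that the protocol leans on 90% power when it interprets a null length-of-stay result. It does not. Section IV.E says the sample may be too small to detect differences in postoperative outcomes, and IV.F promises cautious interpretation. However, IV.E ties the power risk to the borrowed lung cancer data, gives no figures and does not connect unequal groups with power.

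A reader might also infer that serious imbalance is expected. The documents do not show that either. They set a target of 15 per group, nothing prevents closing a group once it is full, and mild imbalance costs little (86.8% at 14:10). What remains is that no balancing mechanism is written down and that the loss becomes material at about 2:1 and beyond.

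**Conclusion.** The point holds, and it is minor. The β label is wrong as printed. With 12 evaluable per group, a 4-day difference, SD 3 and a two-sided 5% level, power is about 88% by the t test or the planned permutation test; 13 per group would reach 90%. With 24 evaluable patients, power falls to 84% at 16:8 and 77% at 18:6.

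These figures assume a two-sided test, roughly normal data with a common SD of 3, and splits chosen for illustration. They do not show that the trial is too small for its purpose as a pilot, or that the 12 was miscalculated. Whether three extra patients per group is enough for attrition is a separate question and is not judged here.

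**What to change.** In the sample-size paragraph of IV.B, replace the β entry and state the sidedness and method. Suggested wording: *Two-sided α = 0.05; power is about 0.88 (β about 0.12) with 12 evaluable participants per group, by two-sample t test, with a similar value for the planned permutation test. Power is lower if the groups are unequal (for example, with 24 evaluable participants, 0.84 at 16:8 and 0.77 at 18:6; illustrative splits).*

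A line on larger SDs may be added if it is labelled as assumed, but the correction does not depend on it.

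The cost is wording only. The stated power becomes slightly less favourable, and neither enrolment nor the analysis changes.

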Hospital length of stay will be collected from medical records and be defined as the number of days from surgical admission to hospital discharge.

Hospital readmission will be assessed as whether a patient is rehospitalized in an unplanned response to a surgical complication within 30 days of hospital discharge. Planned rehospitalizations will not be assessed as a hospital readmission.

Hospital physical function will be assessed using the AM-PAC test of inpatient physical activity and basic mobility³⁰.

Questionnaire/Psychological Outcomes Assessment:

Fatigue will be assessed using the Functional Assessment of Chronic Illness Therapy - Fatigue scale (FACIT-Fatigue), a validate measure of fatigue in cancer survivors³¹.

Health-related Quality of Life (HRQOL) will be assessed with the Functional Assessment of Cancer Therapy-General form (FACT-G)³². This form provides information on the physical, social, emotional, and functional well-being of patients with cancer.

Subjective psychological stress will be assessed with the Perceived Stress Scale (PSS)³³, which assesses *perceived stress* based on individual and environmental stressful events, focusing on experiences in the last month. *Depression* will be assessed using the Center for Epidemiologic Studies Depression Scale (CES-D)³⁴.

Prior physical activity level will be assessed with the Godin Physical Activity Questionnaire. This measure is a self-report estimate of leisure physical activity for the prior month. Prior physical activity level will be compared between groups and considered as a potential factor to control for in statistical analyses. This will only be collected at the first assessment.

Objective Stress Assessment:

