Thirty days after hospital discharge, the participants' electronic health record will be reviewed to retrieve data about initial hospital length of stay and 30-day unplanned hospital readmission. Visit 3 will be performed at approximately 6 weeks post hospital discharge. This is the time at which some patients may begin more chemotherapy or radiation treatment (adjuvant therapy), and Visit 3 will be performed prior to this to avoid confounding effects of the therapy.

Exercise Intervention: Participants will start the exercise program within four weeks of their diagnosis and decision to undergo neoadjuvant treatment and continue until surgery. Participants will continue to receive the standard medical care (described below) provided at UCCC. Individual exercise sessions in this program implement a "whole body" approach and consist of a 10-min cardiovascular warm-up and 50 minutes of cardiovascular endurance, resistance, and flexibility exercises (session components). Typical cardiovascular endurance exercises include walking on an indoor track or treadmill, stationary cycling, and stationary rowing. Resistance training includes exercises using body weight, free weights, and weight machines targeting increased strength of the large upper and lower extremity muscle groups and core stability. Flexibility exercises target major muscle groups activated during the exercise. Target intensity of exercise will be based on the American College of Sports Medicine (ACSM) recommendations for cancer survivors²: 40-85% heart rate reserve for cardiovascular endurance exercises; 60-70% one repetition maximum for resistance exercises; and a rate of perceived exertion of 12-16 on a 6-20 Borg scale for all activities.

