Potential Problems and Solutions: Given that no previous studies of preoperative exercise programs exist in patients with pancreatic cancer, the power analysis for the current study was based on the outcomes of a study of preoperative exercise in patients with lung cancer. It is possible that the estimated sample size here will not provide enough power to detect differences in postoperative outcomes. Regardless of statistical significance, outcomes from this study will provide the basis to allow future studies in this population that are adequately powered. Study groups will not be randomized, resulting in a potential selection bias and baseline differences. The decision to design the study as a non-randomized trial was made to improve recruitment for the target patient population and the short duration of the funding period. Analysis of the number of participants who are willing and able to participate in an exercise intervention at the AHW will determine if a randomized trial is feasible and allow a better estimate of a realistic enrollment period. We will interpret our enrollment activity as

follows: if less than 70% of anticipated enrollment is achieved, we will conclude that additional study sites will be needed to enroll sufficient numbers of patients treated with neoadjuvant therapy for pancreatic cancer for formal hypothesis testing in a RCT.

The individualized nature of the exercise program precludes rigorous control of exercise components between participants. An individualized exercise program may increase adherence and will allow adaptability to acute changes in the patients' health status due to treatment- or disease-related symptoms. The neoadjuvant therapy period will vary between participants, resulting in a variable duration of the exercise intervention. The duration of exercise must remain variable to avoid deconditioning that would be caused by a long lapse between the end of the exercise intervention and surgery. Most patients complete 16 weeks of neoadjuvant therapy before surgery, which will result in a typical exercise intervention lasting 12 weeks. We will record the duration of exercise training and neoadjuvant therapy and test these factors as covariates in the analyses of the fitness, function, and stress outcomes.

F. Data Analysis Plan:

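### The allowance of 3 extra participants per group covers 20% attrition, not the 28% cited as its basis; keeping 12 at 28% loss would take 17 per group.

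*Combined protocol and SAP*

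**What the plan says.** Section IV.B (Sample size estimation) takes a 4-day reduction in hospital length of stay from a lung cancer study and an SD of 3, and concludes that "12 participants would be required in each the experimental and control groups" at α = 0.05 and what is printed as β = 0.90. For attrition, "groups will be increased by 3 participants each, based on a study of preoperative exercise after neoadjuvant treatment" carried out "in patients with rectal cancer showing an overall attrition of 28"%. The stated total is "30 participants (15 per group". No other attrition rate and no inflation formula appear in the document.

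On the outcome that drives the calculation, Section IV.A says "Hospital length of stay will be collected from medical records" and counts it from surgical admission to discharge. Section IV.C repeats that the "electronic health record will be reviewed to retrieve data about initial hospital length of stay".

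Section IV.E concedes that "It is possible that the estimated sample size here will not provide enough power to detect differences in postoperative outcomes", and ties that risk to the use of a lung cancer study for the power analysis. Section IV.F asks for cautious interpretation, as for a pilot. Neither section mentions attrition.

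**The concern.** The paragraph links three figures: 12 needed, 3 added, 28% attrition as the reason for adding them. A reader will conclude that 12 per group would remain after 28% loss. They would not, because 3 is 20% of the 15 recruited.

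What is at stake is the stated power for length of stay under Aim 2, Hypothesis 2. There is a secondary risk: Section IV.E says the results will be the basis for adequately powered later studies, and an allowance worked out this way could be carried into them.

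The same sentence has a labelling slip. Read literally, β = 0.90 means 10% power. It does not affect the attrition point.

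**Working it through.** **Inputs, all from Section IV.B:** difference 4 days; SD 3; α = 0.05; power 0.90 (printed as β); 12 per group required; 3 per group added; 15 per group recruited; 28% attrition cited. Whether the test is two-sided is not stated.

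**1. Reproduce the 12 per group.** Normal approximation, n per group = 2(z_α + z_power)²(SD/difference)².
- Two-sided: 2 × (1.960 + 1.282)² × (3/4)² = 11.82, so 12. This matches the plan.
- One-sided: 9.63, so 10. This does not match.
- Two-sided t test: 12.86, so 13.
- With β literally 0.90: 2 × (1.960 − 1.282)² × (3/4)² ≈ 0.5 per group. Only power = 0.90 gives 12.

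The two-sided normal formula is therefore inferred as the one used.

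**2. Loss that 15 per group can absorb.** (15 − 12)/15 = 3/15 = 20%, provided neither group loses more than 3.

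**3. What remains at 28% loss.** 15 × 0.72 = 10.8 per group; 30 × 0.72 = 21.6, so 21 or 22 of 30.

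**4. Size needed to keep 12 at 28% loss.** 12/(1 − 0.28) = 16.67. Sixteen is short (16 × 0.72 = 11.52); 17 is enough (17 × 0.72 = 12.24). That is 34 in total.

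**5. A possible origin of the 3.** 12 × 0.28 = 3.36, rounded down. This applies the loss to the number required instead of the number recruited. It is an inference; the plan shows no working.

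**6. Power if the loss does remove length-of-stay values.** Two-sided α = 0.05, difference 4, SD 3. Normal approximation: power = Φ(4 / (3√(1/n₁ + 1/n₂)) − 1.960). At 12/12 this is Φ(3.266 − 1.960) = 0.904. The last column is a simulation of a permutation test of the mean difference, assuming normal data (4,000 simulated trials, 999 permutations each, Monte Carlo SE 0.005–0.007).

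| Evaluable per group | Overall loss | Normal | t test | Permutation |
|---|---|---|---|---|
| 12 / 12 | 20% | 0.904 | 0.877 | 0.873 |
| 11 / 11 | 26.7% | 0.878 | 0.845 | 0.835 |
| 10.8 / 10.8 | 28% | 0.873 | 0.837 | – |
| 10 / 11 | 30% | 0.863 | 0.825 | 0.812 |
| 14 / 8 | 26.7%, unequal | 0.853 | 0.816 | 0.808 |
| 15 / 7 | 26.7%, unequal | 0.830 | 0.791 | 0.784 |

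Even at 20% overall loss, an uneven split of 15/9 gives 0.885 by the normal approximation, so the 20% must be read as applying to each group.

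**The case against.** - **The text says the addition is based on the 28% study, not that 28% is the planning rate.** What that study counted as attrition cannot be seen from the protocol. This is fair, but 28% is the only rate given, and nothing explains a reduction to 20%.
- **Length of stay is taken from records, so stopping exercise or missing a visit need not lose it.** This stands, and it is why the power effect is conditional. A participant who never reaches surgery would have no value, but the document gives no rate for that. If neither group loses more than 3 values, there is no shortfall.
- **Seventeen per group keeps 12 only on average.** True. With independent 28% loss, a given group keeps at least 12 with probability of about 67% at 17 recruited and 36% at 15. This qualifies the figure of 17 but does not help the figure of 15.
- **The unequal splits have no basis in the document.** No particular split is supported, and 15/7 is an extreme. But equal loss cannot be presumed either: groups are not randomised, and controls are those "unable to commit to participation in the exercise intervention for practical reasons". The splits show direction and are not forecasts.
- **The plan already concedes low power and is a pilot whose first aim is feasibility.** This limits the weight of the point. It does not repair the allowance, because the concession concerns the borrowed effect and not attrition.

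**Conclusion.** The concern holds, as a minor point. On the plan's own numbers, 15 per group covers 20% loss in each group against the 28% cited; 17 per group would be needed to keep 12 on average. This part needs no assumption beyond reading 28% as the loss to be covered.

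The effect on power rests on further assumptions: that 28% of participants lack a length-of-stay value, that the test is two-sided, and that the 4-day difference and SD of 3 are right. With loss shared equally, the cost is then about 3 to 4 points by the normal approximation (90.4% to about 86–88%). By t test, power goes from 87.7% to about 82–84%. The simulated permutation test, the kind of test the plan specifies, goes from about 87% to 81–84%. Unequal loss costs more. No design decision depends on this.

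**What to change.** Keep 30 participants and restate the allowance in Section IV.B along these lines:

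> *Fifteen per group allows for 20% loss of length-of-stay values in each group. If loss reaches the 28% overall attrition seen in the rectal cancer study and is shared equally, about 21–22 of 30 participants would be evaluable for length of stay. Power for a difference of 4 days with SD 3 at α = 0.05 would then be about 86–88% by the two-sided normal approximation (about 82–84% by a two-sample t test), and lower if loss is unequal.*

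Before adopting this, the sponsor should confirm the sample size formula and that the test is two-sided. In the same sentence as the sample size, change β = 0.90 to power = 0.90 (β = 0.10).

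The cost is wording only. No further patients are needed, and the power stated for 28% loss becomes slightly less favourable than the present text implies.

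### The stated 0.90 power for length of stay needs 12 operated patients per group, but 15 enrolled leaves fewer at the plan's own 28% attrition, and that rate is not shown to cover the neoadjuvant period

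*Combined protocol and SAP*

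**What the plan says.** Sample size (Section IV.B, Sample size estimation). The effect comes from a lung cancer study in which "a preoperative exercise program reduced hospital length of stay by 4 days compared to usual care". The calculation follows: "Based on this difference, with a SD of 3, 12 participants would be required in each the experimental and control groups", with alpha 0.05 and 0.90 printed against beta. Then comes the allowance: "To account for overall attrition, groups will be increased by 3 participants each". The plan gives one source for the size of that allowance, saying that it is "based on a study of preoperative exercise after neoadjuvant treatment in patients with rectal cancer showing an overall attrition of 28" per cent. The total is 30, or 15 per group.

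Outcome (Section IV.A, Postoperative outcomes). Length of stay is taken from medical records and is "defined as the number of days from surgical admission to hospital discharge".

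Timing. The inclusion criteria require a first diagnosis of borderline-resectable disease less than 4 weeks old, with neoadjuvant therapy and surgery assigned. Section IV.C (Exercise Intervention): "Participants will start the exercise program within four weeks of their diagnosis and decision to undergo neoadjuvant treatment and continue until surgery". Section IV.E: "Most patients complete 16 weeks of neoadjuvant therapy before surgery", with a typical exercise period of 12 weeks.

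No section gives an expected proportion reaching surgery or a rate of loss during therapy.

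**The concern.** A participant who is enrolled but never operated on has no length of stay, so the sample size that matters is the number operated on and discharged, not the number recruited. Two things separate the two numbers here.

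- The allowance is smaller than the rate given to justify it.
- The rate comes from a study whose exercise followed neoadjuvant treatment. Participants in this trial must first get through that treatment, and progression, toxicity, withdrawal or cancelled surgery could each remove a length of stay.

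At stake is how the length-of-stay comparison is read. Section IV.F plans a between-group test at 0.05 and anticipates a significantly shorter stay with exercise. If the analysed groups are well below 12, a null result set against 0.90 power would look more informative than it is. Because groups are not randomized, the reader also needs to see whether similar proportions of each group reached surgery.

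**Working it through.** **Inputs.** From Section IV.B: difference 4 days, SD 3, alpha 0.05, 12 per group before attrition, 15 after, cited attrition 28%. Assumed: a two-sided test (sidedness is not stated); the 0.90 is power, since that reading reproduces 12; equal groups. The planned test is an exact permutation test, and t-test power is used as its approximation.

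**1. The plan's own figure.** Normal-approximation formula:

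n = 2 × (1.96 + 1.2816)² × 3² / 4² = 2 × 10.508 × 9/16 = 11.82, rounded up to 12 per group.

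The printed 12 is reproduced. At 12 per group, power is 90.4% by normal approximation and 87.7% by noncentral t (standardized difference 4/3). The t test needs 13 per group to reach 90% (90.3%).

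**2. What 3 extra per group absorbs.** 3/15 = 20%, and 15 × 0.80 = 12. The allowance holds for total loss up to 20%, whatever its cause or timing.

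**3. What the cited rate implies.** 15 × (1 − 0.28) = 10.8 per group. To keep 12 at that rate, 12/0.72 = 16.7, or 17 per group (34 in total), against the planned 15 (30 in total).

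**4. Power by total loss, 15 enrolled per group.** Noncentrality = (4/3) × √(n/2), with 2n − 2 degrees of freedom. Fractional n is an expected number.

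| Total loss | With a length of stay, per group | t-test power | Normal approximation |
|---|---|---|---|
| 20% | 12 | 87.7% | 90.4% |
| 28% (cited) | 10.8 | 83.7% | 87.3% |
| 40% (assumed) | 9 | 75.7% | 80.7% |
| 50% (assumed) | 7.5 | 66.6% | 73.3% |

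The documents give no rate for 40% or 50%; these rows only show sensitivity.

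**5. Power by number operated.** 12 per group: 87.7%; 10: 80.5%; 9: 75.7%; 8: 69.9%.

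**6. Timing, side by side.** Source study, as the protocol describes it: exercise after neoadjuvant treatment. This trial: entry within 4 weeks of diagnosis, exercise until surgery, about 16 weeks of therapy of which typically 12 include exercise. The protocol does not say when the source study enrolled or from what point its 28% was counted, so whether that figure includes losses during therapy cannot be settled from the documents.

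**The case against.** A reader might infer that losses during therapy have no allowance at all. The documents do not support that. The 3 extra per group are for overall attrition, with no limit on cause or timing, and they cover a total loss of up to 20%.

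A reader might also take it as fact that the 28% excludes the neoadjuvant period, and multiply it by a further loss during therapy. The documents do not support that either. They say when the source's exercise took place, not when its attrition count began. Exercise here runs through therapy until surgery, so nothing shows two separate loss phases that compound. Length of stay also comes from records: a participant who stops exercising or misses visits but is operated on may still have a value, so a general attrition rate could overstate the loss for this outcome. For these reasons the working uses total loss only.

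Part of the fall from 0.90 has nothing to do with attrition: the change from normal approximation to t test alone takes 12 per group from 90.4% to 87.7%.

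Finally, the plan is candid about being a pilot. Section IV.E says that power for postoperative outcomes may be inadequate, and Section IV.F promises cautious interpretation. This softens the consequence but does not answer the point. The Section IV.E caveat rests on the effect size having come from lung cancer; it does not mention participants who fail to reach surgery. The gap between 20% and 28% lies within the plan's own figures.

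**Conclusion.** The point holds in a limited form. Fifteen per group does not deliver the stated 0.90 at the plan's own 28% loss: 10.8 per group remain and power is about 84% by t test, or 87% by normal approximation. This needs no outside figure, but it does take the 28% as the share without a length of stay, which may be too high or too low. Beyond that, the plan has no separate or phase-matched allowance for not reaching surgery and does not show that the 28% transfers to a trial that begins near diagnosis. How much larger the shortfall could be is unknown; at an assumed total loss of 40% or 50%, power is about 76% or 67%. All figures rest on the plan's 4 days and SD 3 and on a two-sided 0.05 test. The point bears on a secondary aim of a pilot, but the 0.90 is the stated basis for the sample size and is easily put right.

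**What to change.** In Section IV.B:

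- State that the quantity needed for the length-of-stay analysis is the proportion of enrolled participants who are operated on with a recorded discharge.
- State that the cited 28% has not been shown to cover the neoadjuvant period.
- Replace the single 0.90 with t-test power by number operated per group: 12, 87.7%; 10, 80.5%; 9, 75.7%; 8, 69.9%.

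In Section IV.F, add that the number and proportion operated on in each group will be reported beside the length-of-stay result.

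No increase in enrolment is needed. The cost is a few sentences, one reported line per group, and a less favourable stated power. The proportion operated is also a planning figure that the later, adequately powered study will need.
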